8 QUALITY ASSURANCE AND CONTROL

Quality assurance and quality control is of utmost importance in a randomized clinical trial. Standardized protocols for all measurements have been developed, and adherence to the written protocols is of paramount importance. All data collection personnel will be certified as competent to make the required measurements by trained experts. The following provides an outline of the quality assurance and control program developed for Prevent T2:

- Training and certification of all data collection personnel by experts
- Routine calibration of all equipment following manufacturers guidelines
- Performance of routine clinic site-visits and source document verification

- Setting realistic limits on data entry fields in REDCap
- Remote monitoring of data entry and missing data through REDCap
- Querying appropriate personnel regarding missing data
- Preparing quality control reports for personnel, investigators and medical monitor

9 DATA MANAGEMENT

Assessment (REDCap)

All data collected by the assessment team at SV, BV, and at month 6 and 12 assessment visits will be direct entered to the Research Electronic Data Capture (REDCap) system through data entry by study personnel. Paper forms will be used secondary if direct data entry unavailable (e.g. Internet service failure, power failure, or other equipment failure). REDCap is a secure, HIPAA-compliant, web-based application that can be utilized for electronic collection and management of research and clinical trial data. Study data and electronic data capture tools are housed in a secure data center at UAB, and all web-based information transmission is encrypted. The server is backed up nightly and is protected by an enterprise network security firewall. REDCap will be accessed through the UAB Department of Medicine's secure website, <https://redcap.dom.uab.edu>, where research personnel are required to enter user ids and passwords previously approved and set up by the UAB Department of Medicine REDCap Administrator.

The level of user access and privilege will be determined on an individual basis and will rely upon each user's role in the study and clinics they are associated with. Only select project management personnel will be able to edit participant record IDs or export data; the data collection staff will only be able to view and edit (not export) the participant data and run quality checks for the clinics with which they are associated, and investigators will only be able to view data collected at their site. Only select project management personnel will be able to edit participant record IDs or export data; the data collection staff will only be able to view and edit (not export) the participant data and run quality checks for the clinics with which they are associated, and investigators will only be able to view data collected at their site. All data entered will be run through multiple checks for internal consistency and biologic plausibility; these will be conducted in REDCap with either real-time error messages and data stoppage rules or user-initiated query reports, as well as with study-specific SAS programs designed by the data manager. Missing or questionable data will be assessed and corrected by research staff at the clinics or project management staff at UAB. All users will be thoroughly trained in the use of the REDCap data entry and validation system. Once it is determined that data collection, entry and verification is complete, the REDCap project will be locked so that users will no longer be able to edit the data, but investigators may still export and preserve it.

Intervention – Diabetes Prevention Program (REDCap)

All data collected by the Community Health Workers team over the 12-month intervention will be direct entered to the Research Electronic Data Capture (REDCap) system through data entry by trained Community Health Workers. Paper forms will be used secondary if direct data entry unavailable (e.g. Internet service failure, power failure, or other equipment failure). REDCap is a secure, HIPAA-compliant, web-based application that can be utilized for electronic collection and management of research and clinical trial data. Study data and electronic data capture tools are housed in a secure data center at Vanderbilt University, and all web-based information transmission is encrypted. The server is backed up nightly and is protected by an enterprise network security firewall. intervention delivery, treatment fidelity, scheduling of intervention visits with patients, and tracking of process measures for intervention delivery, such as attendance. REDCap is a secure, HIPAA-compliant, web-based application

that can be utilized for electronic collection and management of research and clinical trial data. REDCap will allow for tailoring the intervention to individual participants, and it will be used by the intervention team to quantify process measures related to intervention delivery. Specifically, it will be used to review participant attendance, goal setting progress, and adherence to the diet and exercise recommendations. These process data will be provided in reports generated and these data can be viewed at the study, clinic, CHW, and participant level.

10 SAFETY AND

This Human Subjects Research meets the definition of a clinical trial.

10.1 POTENTIAL RISKS TO SUBJECTS

Human Subjects Involvement, Characteristics, and Design: Participants will be women and men with obesity and prediabetes who receive care through a network of rural primary care providers and clinics that comprise in part the Primary Care Coalition organized by the UAB Diabetes Research Center. Eligible participants will be women and men aged 19-65 years with obesity (BMI >30) and an hemoglobin A1c (A1c) 6.0% to 6.4% who receive care through one of 4 primary care providers in the Alabama Black Belt. Randomization will occur at the clinic level where participants will be enrolled to either: (1) lifestyle condition only at two practice sites, or (2) lifestyle plus receive metformin 500 mg twice daily prescription from their provider at two different practice sites. All participants will receive the lifestyle intervention of the Diabetes Prevention Program (DPP) plus telemonitoring of their body weight using an Ideal Life body weight scale. The DPP is a 12-month intensive lifestyle modification intervention that include 16 group-based sessions over 6-months and 6 group-based session in the remaining 6-months. Consistent with the DPP, content includes fundamental components of evidence-based lifestyle interventions, including recommendations for dietary modification, increased physical activity, and behavioral strategies designed to promote treatment adherence. The current intervention includes two new features, a telemedicine platform and the participation of community health workers. Participants will be partnered with a Community Health Worker (CHW) who will facilitate the delivery of the group-based session delivered by a trained nurse or dietician joining via the telehealth platform. The CHW will assist participants in setting up the telemonitoring and conduct 16 brief weekly calls and 6 monthly calls over the 12-month intervention. This is a pilot trial designed to test feasibility for a larger scale randomized clinical trial that will evaluate effectiveness of an innovative lifestyle intervention combined with metformin for diabetes prevention.

Inclusion Criteria:

- Age 19 (the age of adulthood in Alabama) to 65 years
- A1c (A1c) 6.0% to 6.4%
- Body mass index (BMI) 30-50 kg/m²
- Receives care at one of the 4 participating primary care clinics
- Resides in one location at least 5 days each week
- Telephone line or Wi-Fi internet connection or cellular signal in home
- Willing or able to partner with a Community Health Worker
- Attend group sessions

Exclusion Criteria:

- Pregnancy or anticipating pregnancy
- Diabetes (A1c $\geq 6.5\%$, and/or chart value of fasting glucose ≥ 126 mg/dl, and/or diabetes medications)
- Unwilling or unable to do any of the following: give informed consent, accept random assignment, allow study staff to visit them at their primary care clinic for two follow-up visits
- Likely to relocate and no longer be seen at primary care clinic in the next 2 years
- Weight loss or gain $\geq 5\%$ of body weight in past 6 months (other than postpartum)
- Prescription weight loss medications within the past 6 months
- Another household member already participating in the study
- Abnormal thyroid status
- eGFR ≤ 60
- not able to ambulate or have end-stage medical conditions with limited life expectancy

Sources of Materials: All material obtained from participants will be used specifically for research purposes. Data to be gathered from participants include self-report questionnaires and weight and height measurements as outlined in the study protocol. A1c will be assessed by finger stick and point-of-care testing in the clinics using CLIA approved devices. We will conduct chart abstraction using the electronic medical records from the participating clinics in addition to data collection by our trained assessment team. Data will be collected from participants by the research team, by trained staff at the primary care clinics, and through the Ideal Life software interface (the scale manufacturer), where weights will be automatically recorded. Only the research team will have login credentials to access information. All data will be available only to trained research staff affiliated with this study.

All outcomes will be assessed using validated scales and tests where they exist. For example, height, and weight will be measured using standard procedures. In addition to direct health measures, several patient-reported outcomes will be measured by questionnaire, including quality of life, physical function, dietary intake, and physical activity.

The assessment team, peer coach, and data management staff will have access to personally identifiable private information about human subjects. All volunteers are assured of their confidentiality both verbally and in the informed consent form. The facilities are strictly limited to the staff of the research institution, clinics and to research volunteers. All medical records are locked in a secure area. Access to these areas is limited to the clinical support staff and the study investigators. Medical records are filed according to identification (ID) numbers. All forms in the chart, with the exception of the consent form and participant contact form, display only the ID number. Electronic data storage is similarly restricted with only the data management staff having access to the databases containing confidential records, i.e. those containing names or identifying information.

Potential Risks

This study does not involve major risks to participants. Efforts to minimize the potential risks of the assessment methods and outcome variables include frequent monitoring by the investigators to assure that no volunteer suffers any adverse effects from participating in the research. Our staff have performed similar testing procedures in many studies. Participants with known serious disease will be excluded from the study.

Potential risks associated with the study procedures include:

- a) Body height and weight. There is minimal risk to participants from these measurements.
- b) Finger stick blood sample. There is the possibility of pain and bruising on the finger where the finger prick is made. Aseptic (sterile) technique and trained personnel minimize these risks.

- c) Diet. Patients may modify their diet based on intervention recommendations that is safe for humans and has been tested repeatedly in clinical trials.
- d) Increased physical activity. Patients in the intervention arm will be counseled to increase physical activity to levels that are consistent with the recommendations for US adults (30 minutes of moderate intensity activity per day). There is the possibility of adverse events such as minor musculoskeletal problems, but risk is minimized by excluding potential participants with contraindications to exercise. Considering these types of events are expected in this trial they will not be recorded or reported unless they meet the definition of a Serious Adverse Event. Patients are counseled to secure physician approval before beginning any new exercise plan.
- e) Gastrointestinal (GI) upset from taking metformin. For patients enrolled in the lifestyle plus metformin recommendations, we will ask patients to monitor their symptoms. Metformin is recommended by the American Diabetes Association for the prevention of diabetes among those at high-risk. To minimize nausea and GI upset, in the Orientation for providers and provider handout on metformin therapy recommendations, materials will describe how to start patients at low dose of 250mg daily and increase to 250mg twice daily after 2 weeks as tolerated. Enrolled participants who do not tolerate metformin (e.g., due to gastrointestinal symptoms) will continue to be followed for 12 months on an intent-to-treat basis. This is a minor risk and is reversible.

Adequacy of Protection against Risks

Recruitment and Informed Consent

The patients are volunteers that will be recruited through the primary care clinics. Potential subjects will then be screened in person to determine that they meet the initial recruitment criteria (such as age and BMI) and have no obvious contraindications to participating in the study. Screening of study participants will be conducted by a trained recruiter following a written manual of procedures. In a one-on-one, the potential participant(s) will be informed of the nature and requirements of the study, either via face-to-face interview or informed consent presentation. All patients will be given time to read the consent form and ask questions one-on-one with research staff. To continue, the participant must read and sign an informed consent to participate in further assessment and treatment.

Protection against Risks

This study will be required to have approval from the UAB Institutional Review Board as well as IRBs at partner institutions. UAB has full accreditation by the Association for the Accreditation of Human Research Protection Programs (AAHRPP). Efforts to minimize the potential risk of the assessment methods include frequent monitoring by the investigators to assure that no participant suffers any adverse effects. All volunteers are assured of their confidentiality both verbally and in the informed consent form. The clinical facilities are strictly limited to the staff of the research institution, clinics and to research volunteers. This is accomplished by a variety of stringent security measures. All medical records are locked in a secure area. Access to these areas is limited to the clinical support staff, director of clinical facilities, and the investigators. Volunteers' medical records are filed according to ID numbers. All forms in the chart, with the exception of the consent form, display only the ID number. Electronic data storage is similarly restricted with only data management staff having access to the databases containing confidential clinical records, i.e. those containing names or other identifying information.

Potential Benefits of the Proposed Research to the Subjects and Others

We cannot ensure direct benefits for patients in this study. However, it is likely that patients in both arms will experience health benefits associated with a healthier diet, increased physical activity and potential weight loss. The results of the study will provide important information about the

feasibility of an innovative intervention delivered through primary care that can be replicated in other regions of the United States.

Importance of the Knowledge to be Gained

This study proposes a comparative effectiveness trial of a pragmatic obesity intervention set within primary care. Thus, there is an urgent need to develop and test pragmatic treatment strategies in the primary care setting. There is a gap between current guidelines and what is currently implemented in clinical practice; thus, feasibility studies are required to change the way that primary care practitioners approach the patients at high risk for developing diabetes. This study directly addresses this gap by testing the feasibility of intensive lifestyle intervention combined with provider recommendations for prescribing metformin.

Pregnancy and Other Exclusions

If a participant experiences a pregnancy lasting beyond the first trimester, her data will be censored from the time of estimated conception, and she will be excluded from further participation. In the case of a miscarriage or pregnancy termination within the first trimester, or if a participant develops another exclusionary condition, such as cancer, unstable angina, or another condition for which weight loss or exercise might be contraindicated, further participation will be determined by the medical monitoring team.

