adaptations of the DPP can be feasible but typically fail to show the same benefit as the more intense original trial version of the lifestyle modification program. The DPP demonstrated benefit from metformin therapy for prevention but to date limited effort has been made to promote the use of metformin therapy for diabetes prevention. Given the urgent need for novel ways to prevent or delay the Type 2 diabetes, this trial will combine the DPP with novel components including telehealth and peer coaches. PreventT2 is a CDC-adapted DPP implemented nationally at a variety of community locations including primary care offices, non-profits, and healthcare organizations (<https://www.cdc.gov/diabetes/prevention/index.html>) PreventT2 will be implemented in both arms of this study to assist participants at high risk of developing diabetes in making lifestyle modifications that may prevent or delay onset of Type 2 diabetes. In this trial, Condition 1 (lifestyle modification only) will be compared to Condition 2 which includes lifestyle modification with the recommendation that the primary care provider consider adding a prescription for metformin. The aim of this study is to introduce novel design elements including telehealth delivery, peer coaches, and daily weight checks to a community-based adaptation of the DPP to enhance research effectiveness. This approach may potentially prove to be a cost-effective and scalable approach to diabetes prevention in the Alabama Black Belt.

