3 OVERVIEW OF STUDY DESIGN

This study is a cluster-randomized, two-arm controlled trial in primary care settings. A total of 4 primary care clinics in rural Alabama will be randomized to either 1) Receive lifestyle modification alone (DPP) or 2) Receive lifestyle modification with metformin therapy recommendations (DPP-recommendations). The sample will include up to 100 adults with obese (BMI 30-50 kg/m²) patients (4 clinics, 25 patients / clinic).

The primary aim of this trial is to conduct a 12-month randomized control trial (RCT) to determine the feasibility of implementing a peer coach-facilitated DPP delivered by telehealth. The DPP will be compared to DPP with metformin therapy recommendations. The goal of the intervention is to prevent or delay the Type 2 diabetes among rural primary care patients with pre-diabetes and obesity at high risk for developing diabetes. The primary outcomes are body weight and HbA1 results at month 12. The RCT will test feasibility and provide data that will inform design and power for a future study to assess diabetes prevention as the main outcome measure. All participants will receive the lifestyle intervention of the Diabetes Prevention Program (DPP) plus telemonitoring of their body weight using an Ideal Life body weight scale. The DPP is a 12-month intensive lifestyle modification intervention that includes 16 group-based sessions over 6-months and 6 group-based sessions in the remaining 6-months. Consistent with the DPP, content includes fundamental components of evidence-based lifestyle interventions, including recommendations for dietary modification, increased physical activity, and behavioral strategies designed to promote treatment adherence. The current intervention includes two new features, a telemedicine platform and the participation of community health workers. Participants will be partnered with a Community Health Worker (CHW) who will facilitate the delivery of the group-based session delivered by a trained nurse or dietitian joining via the telehealth platform. The CHW will assist participants in setting up the telemonitoring and conduct 16 brief weekly calls and 6 monthly calls over the 12-month intervention.

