5 RANDOMIZATION/BLINDING

Randomization. This is a cluster-randomized trial, and enrolled patients at a given clinic will receive the intervention assigned to their clinic. A total of 4 primary care clinics in rural Alabama will be randomized to either 1) Receive lifestyle modification alone (DPP) or 2) Receive lifestyle modification with metformin therapy recommendations (DPP-recommendations).

Blinding. Given that this trial is a small pilot randomized at the clinic level and the interventions are very distinct, patients will know their group assignment, as will clinic staff, CHWs, and research staff that are involved in delivering the intervention.

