6.1.2 DESCRIPTION OF LIFESTYLE INTERVENTION WITH METFORMIN THERAPY RECOMMENDATIONS ARM

Lifestyle intervention program (telehealth + peer coach) with metformin therapy recommendations (DPP-recommendations): Participants will receive the same lifestyle intervention as those in the DPP condition described above. In addition to the lifestyle intervention, they will receive a recommendation for metformin therapy for prevention of type 2 diabetes. Primary care providers at the practices randomized to the DPP-recommendations condition will attend an orientation session and evidence-based materials about low-dose metformin therapy recommendations for patients with pre-diabetes to prevent or delay the onset of type 2 diabetes. At the baseline assessment, study staff will provide participants with the patient education handout on “Understanding Metformin for Pre-diabetes” that details using metformin for prevention of type 2 diabetes. At the same time, the participant’s primary care provider will receive a recommendation to provide their patient with a prescription for Metformin for diabetes prevention. The communication between study staff and PCPs will be developed and

tailored to fit the work flow of each clinic. As described in the inclusion/exclusion criteria, participants without a charted eGFR or an eGFR<60 within the last 6-months will be excluded from the study.

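### The metformin recommendation is stated at two doses that no text connects (500 mg twice daily; 250 mg daily rising to 250 mg twice daily); less seriously, the lifestyle programme has 22 sessions in some sections and 26 in another

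*Combined protocol and SAP*

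**What the plan says.** **Dose.** The arm summary in section 10.1 has two clinics on "lifestyle plus receive metformin 500 mg twice daily prescription from their provider at two different practice sites". Risk item (e) later in that section, and the same item in section 11.1.1.3, say the provider orientation and handout describe how to "start patients at low dose of 250mg daily and increase to 250mg twice daily after 2 weeks as tolerated". Neither place gives a further step or a target dose. Section 6.1.2, which defines the arm, says only that providers get "evidence-based materials about low-dose metformin therapy recommendations for patients with pre-diabetes".

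**Recommendation or prescription.** Section 2.2 describes "the recommendation that the primary care provider consider adding a prescription for metformin". Section 6.1.2 says the "primary care provider will receive a recommendation to provide their patient with a prescription for Metformin for diabetes prevention". Sections 3 and 5 also name the arm by the recommendation. The section 10.1 arm summary instead has participants receiving a prescription at a stated dose.

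**Lifestyle schedule.** Section 3 gives "16 group-based sessions over 6-months and 6 group-based sessions in the remaining 6-months" and has the community health worker "conduct 16 brief weekly calls and 6 monthly calls over the 12-month intervention"; section 10.1 repeats both. Section 6.1.1 gives a total of 26 group sessions, made up of 16 weekly, 4 bi-monthly and 6 monthly, and places a peer-coach contact 1 to 10 days before each one.

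**The concern.** Both arms get the same lifestyle programme. What separates them is the metformin recommendation package: provider orientation and materials, a patient handout, and a message to the provider. The dose is a central part of that package, and the protocol states it in two ways.

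Three things are at stake.

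- **What was tested.** The pilot is meant to inform a larger trial of the lifestyle programme combined with metformin. If the recommended regimen is not fixed in the protocol, the pilot cannot say plainly which regimen its results describe. The text names no metformin prescribing or dose variable: the chart review in section 7 covers unspecified clinical variables, and the process data in section 9 concern attendance, goals, diet and exercise. The ambiguity may therefore be hard to resolve from the data afterwards.
- **What the risk text covers.** Section 10.1 describes the arm at one dose and its gastrointestinal precautions at another. A reader cannot tell which regimen the risk statement addresses.
- **Feasibility measures.** Attendance is one of the process measures in section 9. With two session counts, an attendance rate has no single denominator.

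Prescribing that differs between the two second-arm clinics is possible but not shown. The one provider-facing dose text that the protocol describes is the same in both places.

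**Working it through.** **1. Daily dose**

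| Source | Regimen stated | Daily total |
|---|---|---|
| Section 10.1, arm summary | 500 mg twice daily | 500 × 2 = 1000 mg |
| Section 10.1 item (e) and section 11.1.1.3 item (e), first 2 weeks | 250 mg daily | 250 mg |
| Same items, after 2 weeks as tolerated | 250 mg twice daily | 250 × 2 = 500 mg |
| Section 6.1.2 | low-dose, no figure | not stated |

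There are two readings of the end regimen:

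- If 250 mg twice daily is final, the ratio is 1000/500 = 2.0.
- If it is a step toward the arm-summary figure, the end regimens agree and the ratio is 1.0.

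The documents do not say which applies, so the range is 1.0 to 2.0.

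**2. Group sessions**

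- Section 6.1.1: 16 + 4 + 6 = 26, which reproduces that section's own total.
- Sections 3 and 10.1: 16 + 6 = 22.
- Difference: 4 sessions; 22/26 = 0.846, or 85%; 26/22 = 1.18.
- At full enrolment of 100: 100 × 22 = 2,200 against 100 × 26 = 2,600 participant-sessions, a difference of 400 (400/2,200 = 18%).

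**3. Where the difference falls**

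This depends on the meaning of bi-monthly. At 4.345 weeks per month, 16 weekly sessions take 16/4.345 = 3.7 months.

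- Twice a month: 3.7 + 2 + 6 = 11.7 months, which fits a 12-month programme.
- Every two months: 3.7 + 8 + 6 = 17.7 months, which does not fit.

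On the first reading, about the first six months hold 16 + 4 = 20 sessions under section 6.1.1 and 16 under section 3. The second half holds 6 under both.

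**4. Coach contacts**

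Sections 3 and 10.1 give 16 + 6 = 22 calls. Section 6.1.1 gives a timing rule rather than a count. One contact before each of 26 sessions implies 26.

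**5. What does not change**

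None of these figures enters the precision calculation in section 12 or the models in section 13.

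**The case against.** The strongest reply is that the two dose statements can coexist. Item (e) is about limiting gastrointestinal upset, speaks of how to start patients, and raises the dose as tolerated, so it reads naturally as initiation advice. The arm summary may simply give where prescribing ends up. The provider handout, which is not reproduced, may supply the link.

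This is a fair reading, and it is why the range includes no gap at all. It does not remove the problem. It needs an escalation step that neither item (e) nor its repeat states, and the arm summary mentions no titration. The handout may settle the matter for providers, but the protocol should not depend on it for the content of its randomised component.

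A second reply is that the arm summary is loose shorthand: the prescription comes from the provider, and every other section describes a recommendation. This largely stands as an account of how the wording arose. The compared strategies are defined elsewhere, and the sentence only needs to be brought into line.

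A third reply is that nothing statistical depends on this. Actual prescribing rests with the provider, and participants who do not tolerate metformin are still followed by intention to treat. That is correct, and no effect on sample size or analysis is claimed.

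On the schedule, the reply has more weight. Both arms are affected alike, section 9 defines no attendance rate, the 26 contacts are inferred, and section 3 allows up to 100 participants rather than exactly 100. Those points are why this part is rated lower.

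**Conclusion.** The point holds. As written, the protocol gives the metformin recommendation two doses, 1000 and 500 mg/day, and no text reconciles them. The gap at the end regimen is 2.0-fold if 250 mg twice daily is the final dose and 1.0-fold (none) if it is an unstated step toward the higher figure. The dose conflict alone makes this a must-fix item, because it concerns the component that distinguishes the arms and the regimen that the risk text covers. The clash between receiving a prescription and making a recommendation belongs with it.

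The difference between 22 and 26 sessions is real but of lower severity. It does not by itself bias the comparison between arms. It leaves attendance and fidelity without one denominator, so that a participant who attends 22 sessions scores 100% on one version and 85% on the other. The figure of 400 participant-sessions assumes 100 enrolled, and the placing of the gap in the first half assumes that bi-monthly means twice a month.

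No view is taken on which dose or schedule is right.

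**What to change.** 1. **Dose and arm description (required).** The sponsor and its clinicians should reconcile sections 2.2, 6.1.2, 10.1 (arm summary and item (e)) and 11.1.1.3 item (e) with the provider orientation and handout. One regimen, including any titration, should appear throughout, as should one description of the arm as a recommendation or a prescription.
2. **Lifestyle schedule (lower priority).** Reconcile sections 3, 6.1.1 and 10.1 to one schedule of group sessions and coach contacts, and say what bi-monthly means if the term is kept. Use that session count as the attendance denominator in the process reports described in section 9.

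The cost is a text amendment and a check of the provider materials against it. It adds no patients, visits or procedures, and leaves the sample size and analysis models as they are.
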